6.2.2 Handling of Missing Dates/Months/Years for Concomitant Medications

Prior or concomitant medications with incomplete start dates will be handled as follows for the sole purpose of determining whether a non-study medication is a concomitant medication:

- If the start/stop date of a medication is partially missing, the date will be compared as far as possible with the date of the start of administration of study drug and the date of last dose of study drug plus 30 days. The medication will be assumed to be concomitant if it cannot be definitively shown that the stop date is before the start of administration of study drug, or the start date is more than 30 days after the last date of administration of study drug. The detailed algorithm will be specified in ADaM specifications.
- If the start/stop dates are completely missing, a medication will be considered concomitant.
- If the dose start date is missing for a subject at a data-cut, all non-study medications of the subject will be considered concomitant.

The original partial or missing date will be shown in listings of all non-study medications.

6.2.3 Handling of Missing Dates/Months/Years for Disease History and Prior Therapies

For the purpose of calculating the duration from initial diagnosis, most recent relapse/refractory diagnosis or most recent prior therapy to first dose, partial/missing dates for diagnosis and last prior therapy completion will be imputed as follows:

- If both date and month are missing and the year is prior to the year of screening, the imputed date and month will be 01 July.
- If both date and month are missing and the year is the same as the year of screening, the imputed date will be the middle point between 01 Jan of the year and the screening date. If the middle point falls between two dates, the first of the two dates will be used.
- If date is missing and the month and year are prior to the month and year of screening, the imputed date will be 15th day of the month.
- If date is missing and the month and year are the same as the month and year of screening, the imputed date will be the middle point between the first date of the month and the screening date. If the middle point falls between two dates, the first of the two dates will be used.
- No imputation will be performed if the year is missing.

6.3 Multiple Comparisons/Multiplicity Adjustment

Not applicable since no formal statistical testing will be performed.

6.4 Adjustments for Covariates

Not applicable.

6.5 Subgroups

ORR and PFS will be examined in the following subgroups, if sample sizes allow the analyses:

- Diagnosis (CLL or SLL)
- Gender (Male or Female)
- Age group (<65 or ≥65)
- Race (White or Non-White)

TEAEs (All Causalities) and TEAEs (Treatment-Related) will be examined in the following subgroups:

- Gender (Male or Female)
- Age group (<65 or ≥65)
- Race (White or Non-White)
- Baseline ECOG performance status (0 or 1 versus 2)

More details will be specified in [Sections 7.2.1, 7.2.2 and 7.3.1](#).

6.6 Visit Windows

All data will be categorized based on the scheduled visit at which it was collected. These visit designators are predefined values that appear as part of the visit tab in the eCRF. There will be no additional analysis windowing done based on the assessment date.

6.7 Unscheduled Visits

Unscheduled visits will not be included in by-visit summary tables, unless otherwise specified. For laboratory tests, data from unscheduled visits will be included in listings and summaries of maximum changes from baseline, and the best or worst post-baseline values. For endpoints based on disease status assessment, data from unscheduled assessments will be included in the derivation and analyses of the endpoints.

6.8 Baseline Values

Unless otherwise specified, the baseline value is defined as the value collected at the time closest to, and prior to, the start of study drug administration. Values collected at unscheduled visits prior to the start of the study drug administration will be included in the calculation of baseline values.

6.9 Computing and Coding Standards

Activities will be performed using the following tools:

Table, listing, and figure production	SAS Version 9.2 or higher
Coding	
Adverse Events	MedDRA Version 16.1 or higher

Medical Histories	MedDRA Version 16.1 or higher
Prior and Concomitant Medications	WHODrug Version September 2013
Grading	
AEs	CTCAE Version 4.03
Labs	CTCAE Version 4.03

7 STATISTICAL ANALYSES

7.1 Study Subjects

7.1.1 Disposition of Subjects

The disposition of subjects will include the number dosed based on the AT analysis set.

An end-of-treatment disposition (still on treatment vs discontinued from treatment) will be provided based on the AT analysis set. The primary reason for treatment discontinuation will be included in the table. A listing of these subjects will also be provided, broken down by treatment arm.

An end-of-study disposition (still on study vs discontinued from study) will also be provided based on the AT analysis set. The primary reason for study discontinuation will be included in the table. A listing of these subjects will also be provided, broken down by treatment arm.

7.1.2 Protocol Deviations

Protocol deviations will be assessed during monitoring visits and by data review. At minimum, the following categories of study conduct or data will be assessed for potential protocol deviations: entry criteria, concomitant medications, dosing records, laboratory results, visit schedule and procedures. Protocol deviations will be categorized as major or minor prior to data release for the final analysis of the primary endpoint. A summary table of the protocol deviations will be provided for the AT analysis set. A listing of all protocol deviations will be provided, broken down treatment arm.

7.1.3 Demographic and Other Baseline Characteristics

Demographic variables will be summarized based on AT analysis set. The variables will include age, age group (<65 versus ≥65), sex, race, ethnicity, height, and weight.

7.1.4 Disease History

Disease history will be summarized based on the AT analysis set. The variables will include diagnosis (CLL or SLL), risk factors used for randomization in IPI-145-07 study that are reported on eCRF (high risk cytogenetics [17p deletion: presence vs absence], refractory/early relapse to purine analog based treatment [yes vs no], grade 4 cytopenia(s) [presence vs absence]), years from initial diagnosis to first dose, months from most recent relapse/refractory diagnosis to first dose, stage at initial diagnosis, type of prior treatment, current stage, Binet/Rai stage, and baseline lymphocytes.

The durations to be summarized are defined as follows:

- Years from initial diagnosis to first dose will be calculated as $(\text{date of first dose} - \text{date of initial diagnosis} + 1)/365.25$.
- Months from most recent relapse/refractory diagnosis to first dose will be calculated as $(\text{date of first dose} - \text{date of most recent relapse/refractory diagnosis} + 1) / (365.25/12)$.

The imputation of partial/missing dates is described in [Section 6.2.3](#).

7.1.5 Prior Therapies

Prior therapies (eg, prior to 145-07) will be summarized based on the AT analysis set. The variables will include number of prior systemic therapies (summarized as a continuous variable and as a categorical variable), months from most recent prior therapy to first dose, number and percentage of subjects with prior radiotherapy, and number and percentage of subjects with prior surgery related to primary diagnosis.

The durations to be summarized are defined as follows.

- Months from most recent prior therapy (again, prior to dosing in study 145-07) to first dose will be calculated as (date of first dose – stop date of most recent systemic therapy, prior irradiation or prior surgery +1)/ (365.25/12).

The imputation of partial/missing dates is described in [Section 6.2.3](#). A by-subject listing will be presented for prior systemic therapy.

7.1.6 Medical History

Medical history will be summarized based on the AT analysis set.

Medical history will be summarized by system organ class (SOC) and preferred term (PT) using the number and percentage of subjects who had at least one occurrence of an SOC or PT. The summary will be sorted alphabetically in SOC and by decreasing frequency of PT in the duvelisib arm within an SOC.

7.1.7 Prior and Concomitant Medications

Medications will be considered as prior if they stopped before the date of first dose of study drug.

Medications will be considered concomitant if they were taken at any time between the date of first dose of study drug and 30 days after the date of last dose of study drug, inclusive. If the start date or end date of a medication is completely or partially missing, refer to [Section 6.2.2](#) for the algorithm to determine whether a medication is concomitant.

Prior medications and concomitant medications will be summarized separately. Both summaries will be based on the AT analysis set.

Medications will be summarized by ATC level 1, ATC level 2, and preferred drug name. The summary will be sorted by decreasing frequency in ATC level 1, ATC level 2 and preferred drug name in the duvelisib arm. A subject taking the same drug multiple times will only be counted once.

A listing will be provided for all non-study medications taken on the study. An identifier will be provided to show if a medication is prior or concomitant. Medications that started more than 30 days after the last dose of study drug will be identified as post-treatment.

7.1.8 Exposure to Study Drug

Extent of exposure will be summarized based on the AT analysis set.

Extent of exposure will be summarized for the following variables:

- Duration (weeks): (date of last dose – date of first dose + 1) divided by 7
- Number of cycles started (continuous and categorical)
- Relative dose intensity, defined as 100% x (total dose received)/ (planned cumulative dose for the duration of treatment)
- Number and percentage of subjects with a dose reduction
- Number and percentage of subjects with a dose interruption
- Number and percentage of subjects with study drug discontinued

7.2 Efficacy Analyses

ORR, DOR, and PFS will be derived from investigator assessment.

AT analysis set will be the primary analysis set for all efficacy analyses. If analyses are performed on more than one analysis set, the analyses on the AT analysis set will be considered primary. No treatment comparison between the two arms will be performed and only efficacy endpoints for the duvelisib arm will be tabulated and plotted. Data for both treatment arms will be included in data listings.

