9 STATISTICAL METHODS

Details of the statistical methods for this study will be documented in a Statistical Analysis Plan (SAP). The SAP may modify the statistical methods outlined in the protocol; however, any major modification will also be reflected in a protocol amendment.

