9.4 EFFICACY ANALYSES

ORR, DOR and PFS will be based on response and progression statuses as determined by investigators according to the IWCLL Response Criteria or revised IWG criteria, with modification for treatment-related lymphocytosis.

ORR will be summarized for each treatment arm using a point estimate along with a 95% confidence interval employing the exact binomial method. The proportion of subjects in each response category will also be presented. In the primary analysis of ORR, any subjects not exhibiting a response (eg, CR, CRi, PR, and PRwL) are classified as nonresponders. Additional sensitivity analyses based on other analysis sets or responder definitions may be conducted.

DOR and PFS will be presented for each treatment arm using the Kaplan-Meier method. A 2-sided 95% confidence interval for the median of each of the 2 endpoints will be presented for each treatment arm. Censoring for DOR and PFS will be identical to the method employed for PFS in study IPI-145-07.

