2 STUDY OBJECTIVES

2.1 Primary Objective

The primary objective of this study is to examine the efficacy of duvelisib monotherapy in subjects with chronic lymphocytic leukemia (CLL) or small lymphocytic lymphoma (SLL) who experienced disease progression after treatment with ofatumumab in Study IPI-145-07 and to examine the efficacy of ofatumumab monotherapy in subjects with CLL or SLL who experienced disease progression after treatment with duvelisib in Study IPI-145-07.

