6 GENERAL STATISTICAL METHODS AND DATA HANDLING

6.1 General Methods

Summary statistics will be presented for the duvelisib treatment group, unless stated otherwise.

Unless otherwise specified, descriptive statistics for continuous data will include the number of subjects with data to be summarized (n), mean, standard deviation, median, and minimum and maximum. The same number of decimal places as in the raw data will be presented when reporting the minimum and maximum, one more decimal place than the raw data will be presented when reporting mean and median, and 2 more decimal places than the raw data will be presented when reporting standard deviation.

Descriptive statistics for categorical/qualitative data will include frequency counts and percentages. The total number of subjects in the treatment group will be used as the denominator for percent calculations, unless stated otherwise. All percentages will be presented with one decimal, unless otherwise specified. Percentages equal to 100 will be presented as 100, and percentages will not be presented for zero frequencies.

Descriptive statistics associated with time-to-event analyses will include the number of events, the number of subjects censored, 25% quartile, median, 75% quartile, and corresponding 95% confidence interval for median. These statistics will be presented for all time-to-event analyses, unless stated otherwise.

For listings broken down by center and treatment arm, site (center) number will be ordered by country.

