7.2.1 Analyses of Primary Endpoint

7.2.1.1 Overall Response Rate

ORR will be derived from best overall response (BOR), which is defined as the best time point response that a subject achieves during the course of the study, with the response ranked according to the following order (from best to worst): CR>CRi>PR>PRwL>SD>PD (CRi applies to CLL only).

The estimated ORR (percent of subjects with a BOR of CR, CRi, PR or PRwL) and a 2-sided 95% CI will be provided. The 95% CI will be calculated using exact binomial method. Number and percent of subjects with BOR in each of the response categories (CR, CRi, PR, PRwL, SD, PD) will also be presented. All subjects in the analysis set will be included in the denominator in the calculation of the percentage for each response category or ORR.

Analysis of ORR using the PP analysis set will be provided as a sensitivity analysis.

Subgroup analyses will be performed for ORR using the subgroups specified in [Section 6.5](#).

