8 CHANGES IN PLANNED ANALYSES FROM PROTOCOL

Due to the very small number of subjects (n=8) in the ofatumab treatment arm only results for the duvelisib treatment arm will be tabulated and plotted. Subjects from both treatment arms will be present in the data listings.

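### Ofatumumab efficacy remains half of the primary objective, but the SAP plans no response table, ORR or confidence interval for that arm, only listings

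*SAP*

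**What the plan says.** The objective has two parts. SAP 2.1, following protocol 2.1, covers duvelisib after ofatumumab and also aims "to examine the efficacy of ofatumumab monotherapy in subjects with CLL or SLL who experienced disease progression after treatment with duvelisib". The primary endpoint for both parts is ORR (protocol 3.1, SAP 5.1).

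Protocol 9.4 plans the analysis by arm: "ORR will be summarized for each treatment arm using a point estimate along with a 95% confidence interval employing the exact binomial method". For the time-to-event endpoints it says: "DOR and PFS will be presented for each treatment arm using the Kaplan-Meier method".

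The SAP narrows this in three places:

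- SAP 6.1 sets a default: "Summary statistics will be presented for the duvelisib treatment group, unless stated otherwise".
- SAP 7.2 rules out any comparison between arms and states that "only efficacy endpoints for the duvelisib arm will be tabulated and plotted". Both arms go into the listings.
- SAP 8 declares the departure: "Due to the very small number of subjects (n=8) in the ofatumab treatment arm only results for the duvelisib treatment arm will be tabulated". It is not limited to efficacy, and it too keeps both arms in the listings.

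Protocol 9 sets the rule for such departures: "The SAP may modify the statistical methods outlined in the protocol; however, any major modification will also be reflected in a protocol amendment".

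On safety, SAP 2.2 keeps the evaluation of ofatumumab safety as a secondary objective. SAP 7.3 uses the All-Treated set, which SAP 4.1 defines to include both drugs. SAP 7.3.1 orders the adverse event tables by frequency in the duvelisib arm. It does not say whether an ofatumumab column is shown.

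**The concern.** An objective framed around a response rate needs a planned rate. Nothing in the SAP overrides the duvelisib-only default for ofatumumab efficacy. Followed as written, the plan gives no best-response table, ORR or interval for the second half of the primary objective. A reader of the study report would have to count responders from a listing and compute the interval. Nothing on the page would show how little eight subjects can establish.

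The protocol text supplied still promises the analysis for each arm, so protocol and SAP describe different deliverables for the primary endpoint.

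On safety the question is smaller. Reading SAP 6.1 and 8 together, ofatumumab adverse events are only listed, which leaves a stated secondary objective without a summary. The wording of 7.3 and 7.3.1 does not settle the matter.

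**Working it through.** **1. Objective against output.**

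| Item | Duvelisib | Ofatumumab |
|---|---|---|
| Primary objective (protocol 2.1, SAP 2.1) | yes | yes |
| ORR with exact 95% CI in protocol 9.4 | yes | yes |
| Best-response table, ORR and CI in the SAP (6.1, 7.2, 7.2.1.1, 8) | yes | no |
| Subject listings (SAP 7.2, 8) | yes | yes |

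**2. The plan's own precision figure.** SAP 3.2 and protocol 9.1 say that with 75 subjects in an arm the 95% interval reaches no further than 12 points from the observed ORR. The SAP's method is stated in 7.2.1.1: "The 95% CI will be calculated using exact binomial method". For x responders out of n the exact (Clopper-Pearson) limits are

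- lower = the 0.025 quantile of Beta(x, n − x + 1), or 0 if x = 0
- upper = the 0.975 quantile of Beta(x + 1, n − x), or 1 if x = n

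Over all x from 0 to 75, the largest distance from estimate to limit is 11.96 points, at x = 31. The stated 12 points is reproduced.

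**3. The same method at n = 8 (SAP 8).** The documents do not give the ofatumumab response count, so every outcome is shown.

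| Responders | ORR | Exact 95% CI |
|---|---|---|
| 0/8 | 0% | 0 to 36.9% |
| 1/8 | 12.5% | 0.3 to 52.7% |
| 2/8 | 25% | 3.2 to 65.1% |
| 3/8 | 37.5% | 8.5 to 75.5% |
| 4/8 | 50% | 15.7 to 84.3% |
| 5/8 | 62.5% | 24.5 to 91.5% |
| 6/8 | 75% | 34.9 to 96.8% |
| 7/8 | 87.5% | 47.3 to 99.7% |
| 8/8 | 100% | 63.1 to 100% |

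The zero-responder row can be checked by hand: upper limit = 1 − 0.025^(1/8) = 0.369.

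The largest distance from estimate to limit is at 1/8 or 7/8: 87.5 − 47.35 = 40.15, or 40.2 points. That is about 3.4 times the 11.96 points at n = 75 (40.15 / 11.96).

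**4. Validity at n = 8.** For each true ORR from 0.001 to 0.999 in steps of 0.001, the binomial probabilities of the outcomes whose interval contains that ORR were summed. The smallest coverage is 96.9%. The interval is wide but does what a 95% interval should.

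**5. Safety wording.** Three features hint at a two-arm table: the All-Treated set includes both drugs, 7.3 has no counterpart to the restriction in 7.2, and the sort order names one arm. Against that, 6.1 defaults to duvelisib unless stated otherwise, 7.3 and 7.3.1 do not state otherwise, and 8 covers all tabulated results. The balance favours listings only, without saying so.

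**The case against.** The strongest defence is that the omission is open, reasoned and consistent. SAP 8 is the section for changes from the protocol. It gives the change, the reason and the fallback, and 6.1 and 7.2 agree with it. Protocol 9 allows the SAP to modify methods. The study has no formal sample size calculation and no hypothesis test, and a listing of eight subjects loses no data. An interval such as 15.7 to 84.3% could be said to prove the sponsor's point.

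Much of this stands. Departing from protocol 9.4 is not an error in itself, nothing is hidden, and no decision is shown to turn on the missing row. Eight subjects is a sound reason to omit Kaplan-Meier quartiles and subgroup tables. It does not carry over to a responder count with an exact interval, because that method stays valid at this size and its width is the information a reader needs. Disclosure also does not answer an objective that the same SAP still states.

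Protocol 9 has a second half as well: a major modification is also to appear in a protocol amendment. The protocol supplied still plans the analysis for each arm. The documents do not define major, so whether the clause was triggered is a judgement. Removing one arm's primary-endpoint summary is at least a candidate.

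A reader might also infer that the safety sections contradict each other on ofatumumab adverse event tables. The documents do not support that. No passage promises such a table, SAP 6.1 and 8 both point to duvelisib only, and the All-Treated set is also the primary set in 7.2, where output is duvelisib only. Sorting by the duvelisib arm merely hints at a second column. This is an ambiguity, not a conflict.

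**Conclusion.** The point holds for efficacy. Half of the primary objective has no planned estimate or interval, although the SAP already contains a suitable method. The estimate would be very imprecise: at n = 8 a limit can lie 40.2 points from the observed ORR, against 12 points for the arm of 75 used in the sample size section. It would still say something at the extremes, since 0/8 puts the upper limit at 36.9% and 8/8 puts the lower limit at 63.1%.

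The safety part is secondary: the text is unclear, and its likeliest reading leaves a stated secondary objective with listings only.

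Severity is minor. The duvelisib analyses are untouched, and the data remain available in listings. The conclusion assumes that n = 8 is the number treated with ofatumumab. SAP 3.5 plans two analyses, and the documents do not say that eight is the final count. If it rose to 10 or 12 (assumed values), the largest distance would be 35.6 or 32.2 points and the conclusion would not change.

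**What to change.** In SAP 6.1, 7.2 and 8, add that for the ofatumumab arm best-response counts and ORR as x/n with an exact 95% interval will be tabulated, with n the number treated with ofatumumab at the analysis cutoff. State that the table is descriptive and that no comparison between arms will be made. Say in SAP 8 that the by-arm Kaplan-Meier summaries of DOR and PFS, and the subgroup tables, remain omitted for this arm because of its size. Reconcile protocol 9.4 with the final SAP, or record why the change is not regarded as major.

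In SAP 7.3, state that ofatumumab counts of TEAEs, SAEs and Grade 3 or higher TEAEs will be shown descriptively, and align 7.3.1 with that.

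The cost is a few sentences, one small response table and ofatumumab counts in three adverse event tables. The downside is a visibly wide interval and some temptation to compare arms, which the existing no-comparison statement in 7.2 addresses. Rewording the objective to listings only would also remove the mismatch, but it would require changing protocol 2.1 and would still leave no estimate.
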